9.4.3.2 Review of Safety /SAE Reports

As part of ongoing safety review and obligation to regulatory agencies, cumulative safety and SAE reports will be furnished for each DSMB meeting. These reports will be available to the DSMB, who shall review them in the context of providing additional information to assist the committee's consideration of subject safety.

9.4.3.3 Data Review Meetings

After all subjects enrolled in the Pilot Phase have received the study therapy infusion and been followed for 30 days, the DSMB will conduct a full review of all cumulative safety data before the trial proceeds to the Randomized Phase. As part of the cumulative safety data review meeting for the pilot phase, the DSMB will recommend that the trial proceed to the protocol-specified randomized phase or recommend a dose modification for the randomized placebo study.

Ongoing Monitoring During Randomized Phase

Formal data review meetings that include the entire DSMB will be conducted via teleconference approximately every three months. The timeline for the quarterly DSMB data review meetings will begin after approximately 25% of subjects are enrolled in the randomized phase. Meetings may be postponed due to accrual rates or to coincide with study milestones (e.g. after all subjects' Day 30 data are entered) at the DSMB's discretion. The purpose of the data review is for safety evaluation, and the study may be stopped because of significant safety concerns. SAEs which are related to stopping rules will be continuously evaluated and the full DSMB will be informed of any extra risk.

Other safety data obtained at protocol-specified follow-up visits, including but not limited to data from the assessments listed below, will also be evaluated by the DSMB as appropriate:

- 12-lead ECGs
- Hematology, clinical chemistry, and urinalysis data
- Serum or Urine Pregnancy test
- Medical history
- Physical Exam
- Vital Signs
- FEV-1
- 6 – Minute Walk Test
- QOL Questionnaire
- Adverse Events

The DSMB will evaluate all safety data available for each subject as appropriate. In addition to those assessments listed above, data for DEXA scan, Dobutamine stress echocardiogram test, dynamometer test, and specific biomarkers may be available.

The EMMES Corporation will coordinate the scheduling of the teleconferences to review safety data during the randomized phase.

Open session

Blinded data will be provided to the DSMB approximately 1 week before each data review meeting. The report will contain:

1. Protocol status including any protocol changes
2. Data sources and cutoff dates
3. Analysis methods applied specifically to the open session report
4. Subject enrollment by month
5. Protocol deviations
6. Early treatment discontinuations and study withdrawals
7. Demographic and baseline characteristics
8. Duration of follow-up at time of data cutoff

Closed Session

Only the DSMB members will participate in closed sessions. Unblinded data will be presented to the DSMB in closed session and discussed by the DSMB. "Unblinded" means that the name of actual treatment arm is associated with individual subject data listings and summaries of data. At the chairperson's discretion, the DSMB may discuss or vote on potential study conduct recommendations at closed session.

The closed session report will contain data separated and identified by treatment group. This report (hard copy) will be provided to the DSMB approximately 1 week before each data review meeting and will include:

1. Data sources and cutoff dates
2. Analysis methods applied specifically to the closed session report
3. Subject enrollment
4. Protocol deviations
5. Early treatment discontinuations and study withdrawals
6. Demographic and baseline characteristics
7. Primary and secondary efficacy outcome measures
8. Prohibited concomitant medications
9. Adverse events
10. Serious adverse events

During the closed session, the DSMB chairperson will issue one of the following recommendations as determined by the DSMB and will be reported in the meeting minutes:

1. Continue the study, with or without modifications.
2. Terminate the study for safety concerns.

Separate meeting minutes for the open and closed sessions will be prepared by the DSMB support team, then reviewed and issued by the DSMB chairperson. The DSMB support team will distribute the finalized minutes. The DSMB support team will maintain copies of the meeting minutes for both the open and closed meetings. To preserve the integrity of the study, the detailed rationale and discussion of comparative unblinded data will be included only in the closed meeting minutes

Follow-Up Open Session

Immediately following the closed session, the DSMB will meet with the investigators to discuss any study conduct concerns. This follow-up open session may be attended by DSMB Members, clinical monitor, and study staff. Potential recommendations from the DSMB regarding study discontinuation or continuation, with or without modification, will not be communicated in this open session.

Closed Executive Session

At the discretion of the DSMB chairperson, a closed executive session may be held. Closed executive sessions will include only DSMB members. Discussion of unblinded study data and potential DSMB recommendations and voting may take place in closed executive session. The DSMB may choose whether to write minutes of the closed executive sessions.

9.4.4 DATA FLOW

9.4.4.1 Communications and Reports

For each DSMB meeting, the open session and closed session reports will be prepared by the DSMB support team. Open session reports will be circulated to all attendees of the open session. The closed session reports will be circulated to DSMB members only. The closed session reports will be retrieved from the DSMB members by the DSMB support team and destroyed after the closed session. The DSMB support team will maintain copies of all reports from the open and closed sessions.

9.4.4.2 Review of Unblinding Requests

Except as required by regulatory authorities for safety reporting, individual subjects' treatment assignments will not be unblinded during the conduct of the study, unless a subject safety issue arises in which unblinding is necessary to ensure optimal subject

management. It is not anticipated that unblinding will be necessary, given the hMSCs can be safely discontinued at any time a safety concern arises. The DSMB will be informed in a timely manner of any case for which unblinding was requested and performed.

9.4.4.3 DSMB Additional Analysis Requests

The DSMB may request additional analyses from the statistician if deemed necessary to fulfill the mission of the DSMB. If based on the additional data the DSMB feels there is a need for an unscheduled formal meeting, the DSMB chairperson will arrange.

9.4.4.4 Confidentiality

All documents will be held in strict confidence by the DSMB, and all documents provided to the DSMB will be collected and destroyed at the end of all DSMB meetings by the DSMB support team.

9.4.5 COMMUNICATION

9.4.5.1 DSMB Minutes

The DSMB chairperson is responsible for issuing minutes of the open and closed sessions. Minutes of the open session will be distributed to all open meeting attendees within two weeks of the meeting. Minutes of the closed session will be distributed to the members of the DSMB within two weeks of the meeting. At the conclusion of the study, the DSMB support team will send a complete set of the open and closed reports, minutes of the open and closed sessions with the tables and listings, all presentations and copies of the recommendation forms to the investigators.

9.4.5.2 DSMB Recommendations

Written recommendations will be forwarded to University of Miami/ISCI in the finalized open session meeting minutes within two weeks of the DSMB meeting.

All recommendations of the DSMB, such as a change in the study protocol or early termination of the study, must be documented in the DSMB meeting minutes. If the DSMB recommends modification to, or termination of, the study, the CRO will contact the investigators within 24 hours of the DSMB making the decision.

Recommendations for modifications other than termination should be accompanied by the rationale for the recommendation and the minimum amount of data required to make a decision. The investigator will be responsible for promptly reviewing the DSMB recommendations and determining whether amendments to the protocol or changes regarding the study conduct are required and if reporting to regulatory authorities is warranted (FDA, 2006).

Should there be disagreement between the DSMB and the investigators around the decision to stop or modify the study a separate compliance committee will be appointed. This committee is comprised of individuals who have extensive experience in the pharmaceutical industry and a deep appreciation of the ethical issues surrounding the conduct of clinical studies and are responsible for the investigator's code of ethics. The Compliance Committee is charged with independently evaluating differing opinions that may arise between the investigator and DSMB and applying the highest ethical standards with respect to determining the best interests of subjects enrolled in the study.

10. STUDY ADMINISTRATION

10.1 Regulatory Authority Approval

This study will be conducted in accordance with Good Clinical Practice (GCP) requirements described in the current revision of International Conference on Harmonization of Technical Requirements of Pharmaceuticals for Human Use (ICH) Guidelines and all applicable regulations, including current United States Code of Federal Regulations (CFR), Title 21, Parts 11, 50, 54, 56, and 312 and Title 45, Part 164. Compliance with these regulations and guidelines also constitutes compliance with the ethical principles described in the current revision of the Declaration of Helsinki. This study will also be carried out in accordance with local legal requirements.

10.2 Ethics Approval

It is the Investigator's responsibility to ensure that prior to initiating this study; this protocol is reviewed and approved by the appropriate local IRB. The composition and conduct of this committee must conform to the United States CFR.

The IRB/IEC must also review and approve the site's informed consent form (ICF), other written information provided to the subject and all advertisements that may be used for subject recruitment.

If it is necessary to amend the protocol or the ICF during the study, the Investigator will be responsible for ensuring that the IRB/IEC reviews and approves these amended documents. An IRB/IEC approval of the amended protocol and/or ICF must be obtained in writing before implementation of the amended procedures and before new subjects are consented to participate in the study using the amended version of the ICF.

10.3 Subject Informed Consent

Before being admitted to the clinical study, all subjects must consent in writing to participate. An ICF will be given to each subject, which will contain all United States federally required elements, all ICH-required elements, and Health Insurance Portability and Accountability Act Authorization (HIPAA) information in language that is understandable to the subject.

The process of obtaining the informed consent will be in compliance with all federal regulations, ICH requirements, and local laws.

The investigator or designee will review the study with each subject. The review will include the nature, scope, procedures, and possible consequences of the subject's participation in the study. The ICF and review must be in a form understandable to the subject. The Investigator or designee and the subject must both sign and date the ICF after review and before the subject can participate in the study. The subject will receive a copy of the signed and dated form, and the original will be retained in the site study files. The Investigator or his/her designee must emphasize to the subject that study participation is entirely voluntary and that consent regarding study participation may be withdrawn at any time without penalty or loss of benefits to which the subject is otherwise entitled.

If the ICF is amended during the study, the Investigator must follow all applicable regulatory requirements pertaining to approval of the amended ICF by the IRB/IEC. The site must use the amended consent form for all new subjects and repeat the consent process with the amended ICF for any ongoing subjects.

In cases where a new ICF is issued between the Month 6 (Office Visit) and Month 12 (Telephone visit) the subject will be contacted and informed of the changes. The subject will be asked if they are available to come to the site. If the subject is unable to come to the site the subject may be reconsented via phone.

10.4 Confidentiality of Information

Subjects' names will remain confidential and will not be included in the database. Only subject number, subject initials, and birth date will be recorded in the data system. If the subject name appears on any other document collected (e.g., hospital discharge summary), the name must be deleted before the document is transmitted. All study findings will be stored in electronic databases. The subjects will give explicit permission for representatives of regulatory authorities and the IRB/IEC to inspect their medical records to verify the information collected.

Subjects will be informed that all personal information made available for inspection will be handled in the strictest confidence and in accordance with all state, local, and federal data protection/privacy laws, including, without limitation, the HIPAA.

Subjects will be asked to voluntarily provide written authorization prior to requesting or disclosing private health information either as part of the written ICF or as a separate authorization form. The authorization will contain all required elements specified by 45 CFR 164, and will allow the site to access study-related private health information until the conclusion of the clinical study. The authorization will remain valid and in full force and effect until the first to occur of (1) the expiration of two years after the study therapy is approved for the indication being studied, or (2) the expiration of two years after the research program is discontinued. Individual subject medical information obtained during this study is confidential and its disclosure to third parties (other than those mentioned in this Section) is strictly prohibited. In addition, medical information

obtained during this study may be provided to the subject's personal physician or to other appropriate medical personnel when required in connection with the subject's continued health and welfare.

The investigator will maintain a personal subject identification list (subject and treatment numbers with the corresponding subject names) to enable records to be identified.

10.5 Payments to Subjects and Donors

Subjects will be reimbursed \$25 at the end of each follow-up visit (Month 1 – Month 6) for a total remuneration of \$75. These disbursements are meant to cover the time required to complete these study visits and all necessary travel and parking expenses.

Normal donors for generation of allo-MSC will be reimbursed \$500 at the end of BM aspiration. This payment will compensate donors for lost time, parking, and travel expenses.

APPENDIX 1: Infusion Guidelines

Prior to the start of the infusion the following procedures and assessments will be conducted on the study subject:

1. Vital Signs: Blood pressure, heart rate, respiratory rate, and temperature, will be measured within 15 minutes prior to the initiation of the infusion.
2. Oxygen saturation will be continuously monitored by pulse oximetry for at least 30 minutes prior to initiation of IP infusion.
3. Confirm that IV access is established and that the IV catheter is no smaller than 20 gauge
4. Study personnel needs to verify that the following pre-medications have been administered 30 minutes to an hour prior to infusion, unless otherwise determined by the physician:
 - Hydrocortisone 25 – 50 mg IV
 - Diphenhydramine (Benadryl) 25 – 50 mg IV

Note: No other medications should be given during the infusion unless determined medically necessary by the Investigator.

5. Document pre-medications given prior to infusion on the source documents
6. Required IV Infusion materials as follows:
 - 0.9 % normal saline IV infusion bag
 - IV Pump tubing
 - IV extension tubing (unless using a central line)
 - Volumetric infusion pump
 - Gloves
7. Remove 0.9% normal saline infusion bag and connect IV tubing to the volumetric infusion pump
8. Cover the IV tubing with the blinding material provided with the infusion bag by the drug preparation technician.

During the IP infusion the following procedures and assessments will be conducted on the study subject:

1. Monitor the subject continuously with pulse oximetry
2. Hang the blinded infusion bag. Investigational product (IP) should not be "piggybacked" through another line
3. Intravenously administer the IP at a rate of 2ml/min.
Note: Study personnel administering the IP must be present throughout the infusion process. The Investigator must be available at the site during the infusion process in case an emergency should arise.
4. Record the start time of the infusion bag
5. Gently squeeze the infusion bag several times every 15 minutes to assure uniform dispersion of contents

6. Vital signs and O₂ saturation will be measured every 15 minutes until the end of IP infusion
7. Record the total volume infused from the IP bag
8. At the end of the IP infusion, close the line and flush 25ml of 0.9% normal saline into the luer lock connector on the bottom of the IP bag, reopen line and allow to infuse at a rate of 2mL/min until completion.
9. Discard IV tubing according to established guidelines
10. Return the blinded IP infusion bag to the cell-processing technician.

Procedures post-infusion:

1. Vital signs will be monitored at 15 minutes, 30 minutes, 1 hour, and 2 hours post IP infusion
2. The subject will be monitored for a minimum of 2 hours post IP infusion with continuous pulse oximetry
3. If the O₂ saturation decreases to < 90% over a continual period of 3 – 5 minutes then supplemental oxygen may be added or increased during the two-three hours post-infusion observation period.
4. If at the end of the 2 hour observation period, if a subject's O₂ saturation stays below 90% then the subject will be provided additional oxygen to maintain a saturation of >90% at room air up to 4 hours post infusion.
5. After the minimum two hour observation period, the subject will be continuously monitored and discharged, if no complaints are experienced, such as shortness of breath or other objective signs of cardiorespiratory compromise.
6. Subjects not meeting criteria for discharge will be assessed by the Investigator during the observation period to further determine hospitalization otherwise not specified in the protocol.

Subject Stopping Guidelines:

1. Any subject who develops persistent (that is, still existing more than 3 hours after the end of IP infusion) cardiorespiratory signs or symptoms including hypoxemia (defined per oxygenation criteria of 93% on room air at rest, or shortness of breath, tachypnea, tachycardia, hypotension, or palpitations) will continue with all scheduled follow-up if such follow-up is considered safe in the opinion of the Investigator. The infusion will be stopped if the oxygen saturation does not return to >93% within 3 minutes of initiating supplemental oxygen or if the subject requires greater than 2L/min supplemental oxygen to achieve the required saturation of >93%. If a subject requires the addition of oxygen, it will be continued for 4 hours after the completion of the infusion. At that time, oxygen will be weaned off to maintain a saturation >93% on room air.
2. Any subject whose infusion is stopped due to cardiorespiratory distress will receive no further IP infusions but will continue with all scheduled follow-up if such follow-up is considered safe in the opinion of the Investigator.

3. Any subject who develops any sign or symptom that, at the discretion of the Investigator, warrants the discontinuation of infusion will receive no further IP infusions but will continue with all scheduled follow-up if such follow-up is considered safe in the opinion of the Investigator.
4. Infusion of the IP may be stopped if there is an adverse event that the Investigator believes is related to the IP or if there is an issue with the IP infusion.

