6.4.1. Infusion Monitoring

Subjects will be monitored in the ICU for two hours prior to infusion to establish baseline vital signs (oxygen saturation, heart rate, respiratory rate, blood pressure, and temperature) every 15 minutes. Monitoring will also continue throughout the infusion.

Once the infusion is begun, 2L/min oxygen via nasal cannula will be provided if the oxygen saturation drops below 90% on room air. The infusion will be stopped if the oxygen saturation does not return to >93% within 3 minutes of initiating supplemental oxygen or if the subject requires greater than 2L/min supplemental oxygen to achieve the required saturation of >93%. If a subject requires the addition of oxygen, it will be continued for 4 hours after the completion of the infusion. At that time, oxygen will be weaned off to maintain a saturation >93% on room air.

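### Appendix 1 gives two saturation criteria for the same late post-infusion period, so a subject at 91-92% can meet one instruction and be persistently hypoxemic under another

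*Combined protocol and SAP*

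**What the plan says.** Four places in the protocol deal with saturation during or after the infusion.

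- **Appendix 1, Procedures post-infusion, items 3-4.** Supplemental oxygen may be added or increased if saturation falls below 90% for 3-5 minutes. For a subject who stays below 90% at the end of the 2-hour observation, "then the subject will be provided additional oxygen to maintain a saturation of >90% at room air up to 4 hours post infusion".
- **Appendix 1, Subject Stopping Guidelines, item 1.** Persistent signs are those lasting more than 3 hours after the infusion ends. They include hypoxemia, "defined per oxygenation criteria of 93% on room air at rest". Oxygen, once needed, runs for 4 hours after the infusion and is then weaned to above 93% on room air.
- **Section 6.4.1.** Oxygen during the infusion "will be provided if the oxygen saturation drops below 90% on room air", and "The infusion will be stopped if the oxygen saturation does not return to >93% within 3 minutes of initiating supplemental oxygen". It is continued for 4 hours, and then: "At that time, oxygen will be weaned off to maintain a saturation >93% on room air".
- **Sections 8.2.1 and 8.2.4.** Section 8.2.1 asks for at least 93% in one sentence and above 93% in another. Section 8.2.4 repeats stopping guideline 1, but its list of example signs has neither hypoxemia nor a saturation value.

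Addenda A-D refer to both 6.4.1 and Appendix 1 for infusion monitoring, and to 8.2.4 for stopping guidelines.

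**The concern.** Two instructions in one appendix apply different saturation levels to the same subject over part of the same period. Staff working from item 4 would regard a reading just above 90% as on target. Staff working from stopping guideline 1 would record the same reading as persistent hypoxemia. Item 4 also cannot be followed literally, because a subject receiving additional oxygen is not on room air.

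Three things are at stake: when oxygen ends, how readiness for discharge is judged, and whether persistent hypoxemia is recorded alike across subjects. Discharge in Appendix 1 depends on the absence of complaints or objective cardiorespiratory signs, with no saturation value, so whether 91-92% counts against discharge depends on which line is read. In a trial whose primary objective is safety, the DSMB needs this event classified in one way.

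**Working it through.** No sample size, error rate or event count is involved, and the plan states no figure to reproduce. The check sets the criteria and their time windows side by side.

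| Place | Saturation criterion | Time after end of infusion |
|---|---|---|
| Appendix 1, post-infusion item 3 | below 90% for 3-5 minutes: oxygen may be added or increased | 2-3 hour observation period |
| Appendix 1, post-infusion item 4 | below 90% at 2 hours: oxygen to hold above 90% | 2 hours, up to 4 hours |
| Appendix 1, stopping guideline 1, definition | 93% on room air, no inequality | persistent if beyond 3 hours |
| Appendix 1, stopping guideline 1, weaning | above 93% on room air | from 4 hours |
| Section 6.4.1, weaning | above 93% on room air | from 4 hours |
| Section 8.2.4, item 1 | none | persistent if beyond 3 hours |

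**Step 1: overlap in time.** Item 4 covers 2 to 4 hours and guideline 1's persistence starts after 3 hours. Both apply from just over 3 hours to 4 hours.

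**Step 2: overlap in saturation.** Item 4 is met above 90%. Guideline 1, read as below 93%, is met by anything under 93%. Both hold above 90% and below 93%, which in whole-number readings is 91% and 92%. If the missing sign were at or below 93%, then 93% would join them. Under either reading the overlap is not empty.

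**Step 3: a subject on item 4 oxygen.** A subject below 90% at 2 hours is given oxygen and reaches 91-92% between just over 3 hours and 4 hours. Item 4 is satisfied, and guideline 1 calls the subject persistently hypoxemic.

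**Step 4: the same subject at 4 hours.** The weaning target in guideline 1 and 6.4.1 is above 93%, so 91-92% meets item 4 and misses that target. The durations also differ: item 4 sets an upper limit of 4 hours, whereas guideline 1 and 6.4.1 continue oxygen for 4 hours and then wean.

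**Step 5: a subject never on oxygen.** A subject at 91-92% on room air throughout never falls below 90%. Items 3-4 do not apply, yet guideline 1 classes the subject as hypoxemic beyond 3 hours.

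**Step 6: the other sections do not settle it.** Section 8.2.4 gives no saturation value, and 8.2.1 treats a reading of exactly 93% in two ways.

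**The case against.** The best counter-argument is that these lines serve different purposes and that little follows from the label. Much of this stands.

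- **Section 6.4.1.** A reader might infer that 6.4.1 imposes 93% throughout the 2-4 hour period. It does not. Its weaning target starts at 4 hours, and its other 93% values govern the running infusion. Within the period, the conflict is with guideline 1's definition; 6.4.1 enters at 4 hours.
- **Trigger and recovery level.** Giving oxygen below 90% and requiring recovery above 93% during the infusion is not in itself a contradiction.
- **Stopping, admission, toxicity, endpoint.** A reader might infer an effect on all four. The infusion-stop rule is the same in 6.4.1, 8.2.1 and Appendix 1. Section 8.2.1 ties admission to a stopped infusion. Infusional toxicity is evaluated only until 2 hours after the infusion (8.2.3), before the overlap begins. The TE-SAE composite in 2.2.1 has no saturation term.
- **Consequence of the label.** Guideline 1 says only that follow-up continues if considered safe. Section 8.2.4 adds that further infusions are left to the investigator's judgment, and its list of signs is illustrative, so it does not exclude hypoxemia.
- **Pre-infusion monitoring.** A reader might infer a second contradiction here. Section 6.4.1 says "Subjects will be monitored in the ICU for two hours prior to infusion to establish baseline vital signs", with checks every 15 minutes. Appendix 1 says "Oxygen saturation will be continuously monitored by pulse oximetry for at least 30 minutes prior to initiation of IP infusion", and that vital signs "will be measured within 15 minutes prior to the initiation of the infusion". Both can be met at once: two hours of 15-minute checks, continuous oximetry over at least the last 30 minutes, and the last set of vital signs within 15 minutes of the start. At most, Appendix 1 is an incomplete checklist.

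These points narrow the consequence. They do not reconcile item 4 with guideline 1.

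**Conclusion.** The contradiction is real and confined to the post-infusion period. It concerns readings above 90% and below 93%, from just over 3 hours to 4 hours for item 4 against the hypoxemia definition, and at 4 hours for item 4 against the weaning target. It applies to every infusion in the main phase and Addenda A-D, though only subjects with readings in that band are affected. The documents give no basis for estimating how many that will be.

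The conclusion rests on three assumptions. Guideline 1's unsigned 93% is read as below 93%. Item 4's room-air wording is taken at face value; if item 4 readings were taken on oxygen, they could not be compared directly with guideline 1's room-air criterion, and that ambiguity is itself part of the defect. The 4-hour and weaning sentences are taken to cover oxygen first given after the infusion, since guideline 1 speaks of any subject who needs oxygen.

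This should be corrected because it is a working safety instruction, but it does not threaten the primary analysis.

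**What to change.** Reconcile Appendix 1 post-infusion items 3-4 and stopping guideline 1 with sections 6.4.1, 8.2.1 and 8.2.4, so that one set of saturation criteria and times applies after the infusion. In that revision:

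- print the inequality in guideline 1, and use one inequality in 8.2.1;
- reword item 4 so that it is clear whether the reading is taken on oxygen or on room air;
- make the copies of the stopping guideline in 8.2.4 and Appendix 1 agree on whether hypoxemia is included and how it is defined;
- use that one definition when recording persistent hypoxemia for the DSMB.

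Which values and times apply is for the sponsor's clinicians. A cross-reference from the pre-infusion part of Appendix 1 to 6.4.1 would help but is optional. The cost is protocol wording. Addenda A-D work by reference, so they need no separate rewriting on this point.
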